### 3.2 Exclusion Criteria

Potential participants will be excluded if they meet one or more of the following exclusion criteria:

**Table 3: My-AHA RCT exclusion criteria for participant screening**

EXCLUSION CRITERIA	Participant excluded if meets 1 or more of below:
Mobility problems	
 
1. cannot stand and ambulate unassisted
 
2. painful arthritis, spinal stenosis, amputation, or painful foot lesions that limits balance and mobility,
 

Concurrent chronic disease independently contributing to frailty	
 
1. suffers from a significant neurodegenerative CNS disorder, e.g. 
 
a. Alzheimer's disease
 
b. Lewy body dementia
 
c. Frontotemporal Lobar Degeneration, Fronto-Temporal Dementia
 
d. Parkinson's disease
 
e. multiple sclerosis
 
f. progressive supranuclear palsy
 
g. amyotrophic lateral sclerosis
 
h. hydrocephalus
 
i. Huntington's disease
 
j. prion diseases
 
 
 
2. affected by severe peripheral nervous system and/or neuromuscular disorders, e.g. 
 
a. CIDP
 
b. myasthenia gravis
 
c. multiple sclerosis
 
d. polymyositis
 
 
 

Concomitant injury or disease known to impact independently, cognitive psychological or physical function	
 
1. clinical evidence or history of stroke (within 2 yrs)
 
2. clinical evidence or history of transient ischemic attack (within 6 months)
 
3. significant head injury with associated loss of consciousness, skull fracture or persisting cognitive impairment (2 years)
 
4. epilepsy (a single prior seizure is considered acceptable)
 
5. if meet DSM-5 criteria for: 
 
a. major depressive disorder (current)
 
b. schizophrenia or other psychotic disorders (lifetime)
 
c. bipolar disorder (within the past 5 years)
 
d. substance (including alcohol) related disorders (within the past 2 years)
 
 
 

Presence of cognitive, sensory or perceptual deficits that interfere with assessment tasks	
 
1. have language deficits that impair testing
 
2. have significant visual impairment
 
3. have a significant hearing loss
 

---

*Presence of other conditions or diseases that will compromise participants' ability to undertake interventions (especially physical)*

1. have clinically significant cardiovascular disease, i.e:
  - a. hospitalization for acute coronary syndrome (acute myocardial infarction or unstable, angina)
  - b. symptoms consistent with angina pectoris, within the 12 months
  - c. signs or symptoms of clinical heart failure within the 12 months
  - d. evidence of uncontrolled atrial fibrillation
  - e. a cardiac pacemaker
2. preexisting or current signs or symptoms of respiratory failure, e.g.
  - a. chronic obstructive pulmonary disease
  - b. bronchial asthma
  - c. lung fibrosis
  - d. other respiratory disease
3. untreated hypertension
4. metastatic cancer or immunosuppressive therapy
5. concurrent acute or chronic clinically significant immunologic, hepatic (such as presence of encephalopathy or ascites), or endocrine disease (not adequately treated).

---

*Unacceptable Test/Laboratory Values*

1. Postural hypotension (fall in systolic blood pressure of greater than 30 mmHg or fall in diastolic blood pressure of greater than 20 mmHg on standing compared to sitting) at the time of screening. Participants who present at the time of screening with postural hypotension yet have no known history of postural hypotension, nor underlying medical condition related to hypotension, may be rescreened

---

**Table 4: Exclusion criteria for clinically significant deficits in Cognitive and Psychological function**

Clinical sign/symptom		Measure	Cutoff values	
COGNITIVE DOMAIN	Must NOT meet 1 or more of the EXCLUSION CRITERIA		INCLUSION CRITERIA	EXCLUSION CRITERIA
1. Evidence of lowered general cognitive function	Mini Mental State Examination test (MMSE) screens for deficits across several cognitive functions.	Age-adjusted MMSE 
 
• 24-30 (no cognitive impairment)
 
	Age-adjusted MMSE score 
 
• 18-23 = MCI
 
• 0-17 = severe clinical deficit
 
	
2. Evidence of lower than age-appropriate learning and recall of verbal information	Hopkins Verbal Learning Test (HVLT) is a brief test of verbal list learning and memory. Comprises 12 words, organized into three semantic categories, and presented over three consecutive learning trials.	HVLT-total recall score 
 
• Score <math>\geq 25</math>
 
	HVLT-total recall score 
 
• Score <math>\leq 24</math>
 
	
PSYCHOLOGICAL DOMAIN	Must NOT meet any EXCLUSION CRITERIA		INCLUSION CRITERIA	EXCLUSION CRITERIA
1. Increased levels of anxiety and/or lowered mood experienced over the preceding week	HADS – Hospital and Depression Scale, a 14-item scale to which participant indicates degree of agreement/frequency of experience in previous week on a 4 point scale. Seven of the items relate to anxiety and seven relate to depression.	Scores are computed separately for the Anxiety scale (7 items – HADS-a) and the Depression scale (7 items – HADS-d): 
 
0-7 = normal mood
 
8-10 = mild symptoms
 
11-14 = moderate symptoms
 
	
 
• Scores <math>\geq 15</math> - HADS-d and/or
 
• Scores <math>\geq 15</math> - HADS-a
 
	

### 3.3 Screening Failures

Screen Failures are defined as participants who sign a Screening Participant Informed Consent Form (PICF-Screen) for My-AHA study but are not subsequently randomized and who do not enter the RCT. Participants who are Screen Failures may be rescreened once only after approval by the study Medical Supervisor (University of Torino, Italy).

### 3.4 Withdrawal Criteria

#### 3.4.1 *Reasons for Withdrawal*

- Any clinical AE, laboratory abnormality, or other medical condition or situation occurs such that continued participation in the study would not be in the best interest of the participant in the opinion of the investigator
- Significant protocol violation
- Participant requests to discontinue for any reason; it is important to determine whether the withdrawal of consent is primarily due to an AE, lack of efficacy, or other reason

The above reasons do not automatically lead to withdrawal from the study in all cases. The final decision will be based on consultation between the Principal Investigator and the study Medical Supervisor (University of Torino, Italy), with the ultimate decision by the principal investigator or participant. Participants may discontinue from treatment with study intervention but may agree to continue to be followed for additional safety evaluation.

If a participant meets discontinuation criteria during treatment, the participant will undergo the Participant Withdrawal process (Section 3.4.2).

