#### 3.4.2 *Participant Withdrawal Procedures*

If a participant is prematurely discontinued from the intervention, the investigator must make every effort to perform the evaluations scheduled for the next assessment phase scheduled for that participant.

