#### 4 Participant randomization

Participants will be randomized into 2 study arms, with 50% of participants allocated to each arm:

- Study Arm 1: Control group (n = 25)
- Study Arm 2: My-AHA intervention group (n = 25)

Randomization will occur at each study site independently.

Initial randomization of participants at each site will occur on a 1 (control) : 1 (intervention) ratio, with allocation of participants to each treatment arm being undertaken using an alternating allocation sequence based on order of entry into the study (i.e. participant 1 – study arm 1; participant 2 – study arm 2; participant 3 – study arm 1; participant 4 – study arm 2, and so on).

Once recruitment and allocation to study arms of 20 participants has occurred at each site. The study site PI will submit to the RCT Study Coordinator basic demographic information on the 20 participants recruited and allocated to study arms. The demographic information required for each of the 20 participants is:

- Gender
- Age
- Highest education level

The RCT study coordinator will review the balance of participants across study arms for these demographic variables within each study site and advise the Principal Investigator of any adjustment to the allocation procedures for remaining participant assignment to treatment arms to ensure equivalence of study arms within each site.

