## 7 My-AHA Interventions

The intervention in this study is defined as the My-AHA platform. Participants randomized into the intervention arm will have access to the full My-AHA intervention platform (see also Section 8 My-AHA User Platform interface). Participants in the control group will not have access to the intervention package (no treatment control). All participants recruited into the study have no active disease state being treated. All participants meet study criteria for pre-frail status, a non-clinical disease state.

The protocol in the intervention arm is designed to prevent deterioration from a non-clinical state (pre-frail) into the disease state (frail).

The no-intervention control arm will not receive any element of the My-AHA intervention, a no-intervention non-disease control group. Participants in both study arms undergo formal assessment of clinical frailty status at 4 timepoints (baseline, 6 mo, 12 mo, 18mo). **Development of clinical frailty is considered an adverse endpoint for the participant in this study.**

Where a control group participant displays evidence of clinical decline at 6 or 12mo assessment points (defined as meeting clinical criteria for frailty) they will be offered access to the My-AHA intervention suite. We cannot estimate or predict what proportion of the control participants may develop frailty during the 18 month trial as there is no published data on incidence, age-dependent prevalence, or on average rate of decline into frailty from pre-frail states.

Participants randomly allocated to the intervention group will be provided with access to tailored intervention packages. Intervention packages will target domains of pre-frailty (e.g. physical, social, cognitive, nutrition) identified at baseline assessment for each participant. The intervention packages will be revised following each assessment point to accommodate for changes in domain specific areas of pre-frailty.

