### 7.1.3 Endurance exercise programs

The endurance training exercise programs will be delivered in accordance with the guidelines of the American Heart Association and the American College of Sports Medicine for endurance training for older adults [18] and aims to reach the proposed recommendations of physical activity (150 min/week) by Month 9 of the RCT. The walking part of the OEP will be replaced by an endurance training suggested to be undertaken for one session per week, with the endurance training activity to be selected by each participant to increase compliance (e.g. walking, Nordic walking, bicycling, treadmill or stationary bicycling). Intensity of the endurance training will start at a moderate level the first few months before gradually increasing to vigorous level activity adjusted for the participants' estimated maximum heart rate (HRmax = 220bpm - age). The intensity rate (HRMax) to training duration is specified in Table 7. Participants are able to halt intensity increases if they perceive the level of intensity is too difficult. However, participants will be required to maintain a minimum of 65% of the HRmax for at least 150 Min per week.

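### An undefined protocol-violation ground for leaving the study, with only the next assessment protected, opens a route to losing later outcomes mainly from the intervention arm

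*Protocol*

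**What the plan says.** Protocol Section 3.4.1 gives three reasons for withdrawal: an adverse event or other situation in which continuing is not in the participant's interest, "Significant protocol violation", and the participant's own request. The second has no definition, example or threshold, and it is not limited to either arm. The section then says: "The above reasons do not automatically lead to withdrawal from the study in all cases". The decision follows consultation with the study Medical Supervisor, "with the ultimate decision by the principal investigator or participant". People who stop the intervention "may agree to continue to be followed for additional safety evaluation".

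Section 3.4.2 covers a participant discontinued early from the intervention: "the investigator must make every effort to perform the evaluations scheduled for the next assessment phase scheduled for that participant". It does not mention the assessments after that one.

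Obligations differ by arm. Sections 7.1.1 to 7.1.3 give intervention participants weekly home, group and endurance sessions, and Section 7.1.3 adds that "participants will be required to maintain a minimum of 65% of the HRmax" for a stated weekly time. Section 6.3 has the platform log every complete and incomplete session. Under Section 7, controls receive no intervention and are assessed at baseline, 6, 12 and 18 months, as the intervention arm is. A control who becomes physically frail at 6 or 12 months is given the physical package.

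**The concern.** Adherence is observed after allocation and is partly a consequence of the arm. A rule that lets participants leave the study because of their conduct after allocation can undo the balance that allocation was meant to provide. Here there is much more conduct to breach, and more of it on record, in the intervention arm. The person with the final say is not stated to be blinded. Section 4 allocates by alternation in order of entry, and the comparator is no treatment, so the arm would ordinarily be known.

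If the participants removed are those who were declining, the intervention participants still under assessment are a healthier subset set against a nearly complete control arm. Progression to frailty would then look rarer on the platform even if it did nothing. A statistical analysis plan can decide how to use data that were collected. It cannot recover 12 and 18 month assessments that were never made.

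**Working it through.** **The plan's own figures.** The protocol gives no frailty rate, and Section 7 says the proportion of controls who become frail cannot be predicted. Nor does it give an expected adherence or withdrawal rate. The only figure that can be checked is the sample size: 25 + 25 = 50, which agrees with Section 2.1. The numbers below are therefore illustrations.

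**Step 1: which outcomes are exposed.** Set Section 3.4.2 against the assessment schedule:

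| Removed | Assessment still sought | Assessments not protected |
|---|---|---|
| Before 6 months | 6 months | 12 and 18 months |
| Between 6 and 12 months | 12 months | 18 months |
| Between 12 and 18 months | 18 months | none |

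The 18 month outcome is exposed only for removals before the 12 month assessment.

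**Step 2: size of a possible distortion.** Assume the platform has no effect. Let p be the overall frailty risk in each arm, q the share of non-adherers in the intervention arm, and r the risk ratio of non-adherers to adherers. Then

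p = (1 − q) × a + q × r × a, so the adherers' risk is a = p / ((1 − q) + q × r).

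If every non-adherer is removed and contributes no outcome, the intervention arm shows a and the control arm shows p. With p = 30% and q = 20% (5 of 25):

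- r = 1: 0.30 / (0.80 + 0.20) = 30.0%, difference 0
- r = 2: 0.30 / (0.80 + 0.40) = 25.0%, difference −5.0 points
- r = 3: 0.30 / (0.80 + 0.60) = 21.4%, difference −8.6 points

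**Step 3: range.** Risk shown in the intervention arm at p = 30%, against 30% in controls:

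| Share removed | r = 1 | r = 1.5 | r = 2 | r = 3 |
|---|---|---|---|---|
| 8% (2 of 25) | 30.0% | 28.8% | 27.8% | 25.9% |
| 20% (5 of 25) | 30.0% | 27.3% | 25.0% | 21.4% |
| 30% (7 to 8 of 25) | 30.0% | 26.1% | 23.1% | 18.8% |

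The spurious risk ratio is 1 / ((1 − q) + q × r), which does not depend on p. At q = 20% it is 0.91, 0.83 and 0.71 for r = 1.5, 2 and 3. At p = 15% and q = 20% the intervention arm would show 13.6%, 12.5% and 10.7% against 15%.

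For given q and r, when r is above 1, these figures are the far end of what one-sided removal could do. They assume that every non-adherer is removed, that none is assessed again, and that no control is withdrawn.

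**The case against.** The strongest reply is that a bias is being inferred from a short, conventional list. Several parts of that reply stand.

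- **Non-adherence is not called a violation.** No passage attaches withdrawal to missed sessions, heart-rate level or app use. Section 6.3 and Table 6 treat adherence as something to measure, and Section 7.1.3 lets participants halt increases in intensity. This is correct. However, nothing excludes non-adherence either, and falling short of a stated requirement is a natural reading of an undefined term. Section 7.1.3 also states its 65% minimum without a start month, while Table 7 schedules 50% to 60% through month 8. Those passages must be reconciled, because on one reading a participant who follows the table would be in breach.
- **The ground covers both arms.** Controls can have eligibility errors or missed assessments, and Section 3.4.2, worded around stopping the intervention, does not plainly cover a withdrawn control. A reader might infer that participants can be removed from one arm only. The text supports a difference of degree, not that.
- **Withdrawal is neither automatic nor decided alone.** It needs consultation with the Medical Supervisor. That is a check, but it supplies no criterion, and discretion with the arm known does not prevent selection.
- **The next assessment is still sought.** Outcomes are therefore not all lost. A reader might also take follow-up after stopping to be for safety alone, but Section 3.4.1 does not say so.
- **The analysis population may be set elsewhere.** Nothing in the protocol says that data from withdrawn participants are dropped. This answers a charge about the analysis, but not one about assessments that are never made.

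**Conclusion.** The point holds as a weakness in a conduct rule. An undefined ground for leaving the study, discretion without stated blinding, unequal obligations and protection of a single assessment together allow later outcomes to be lost predominantly from the intervention arm.

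A reader might go further and conclude that the comparison is biased towards the platform. The documents do not support that. Whether any bias arises depends on how the ground is used, how early removals occur, and whether those removed have a worse prognosis. With equal prognosis the distortion is zero. Under the assumptions shown (no true effect, 30% risk, 5 of 25 removed with no outcome), it is 5 points at a risk ratio of 2 and about 9 points at 3. None of these inputs comes from the protocol. The change is still worth making, because in an arm of 25 a few removals matter and the missing assessments could not be recovered at analysis.

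**What to change.** 1. In Section 3.4.1, remove "Significant protocol violation" as a ground for leaving the study.
2. State instead that violations in either arm, including non-adherence and eligibility errors found after allocation, are recorded as deviations with reason and arm, and do not by themselves end outcome follow-up.
3. In Section 3.4.2, extend the effort from the next assessment to all remaining scheduled 6, 12 and 18 month assessments, and word it for both arms.

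Leave the adverse-event and participant-interest bullet and the participant-request bullet as they are. Restricting study withdrawal to withdrawn consent would override the participant-interest bullet and is not proposed.

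The cost is an edit to two short sections and a few more assessments that are already in the schedule. The effect estimate will include non-adherers and may look smaller.

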#### 3.4.2 *Participant Withdrawal Procedures*

If a participant is prematurely discontinued from the intervention, the investigator must make every effort to perform the evaluations scheduled for the next assessment phase scheduled for that participant.

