	LSNS-R (Lubben Social Network Scale, Short form)	✓	✓	✓	✓
Social	UCLA Loneliness Scale	✓	✓	✓	✓
	BMI ( derived from height/weight data in Physical battery )	✓	✓	✓	✓
	Self-MNA	✓	✓	✓	✓
Technology	Evaluation of Usability Scale (SUS)				✓
	DART questionnaire				✓
	Computer Literacy Scale (CLS)			✓	
	User Experience Questionnaire (UEQ)				✓
Measures used to determine pre-frailty status of participants (see Table 2)					
Estimated maximum protocol duration:					

 
• Screening assessment – 60 min (1hr)
 
• Baseline assessment – 155 min (2hr 35min)
 
• 6 month assessment – 130 min (2hr 10 min)
 
• 12 month assessment – 135 min (2hr 15 min)
 
• 18 month assessment – 155 min (2hr 35min)
 
					

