### 6.4.2 Brief demographic questionnaire

At follow-up assessment time points (6, 12, 18 months) the *Brief Demographic Questionnaire* (Appendix 6) is to be completed by each participant. This questionnaire is designed to collect data on demographic variables that may change across the duration of the RCT, specifically information regarding changes in:

- Change in residential status since last assessment
- Current fear of falls
- Falls history since last assessment
- Cognitive activities (mental activity) engaged in since last assessment
- Medical since last assessment point (diagnoses existing and new, medication prescription current)
- Continence/incontinence

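### Section 3.4.2 requires only one further assessment after a participant stops the intervention, so 18-month outcomes, and some 12-month outcomes, may never be collected

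*Protocol*

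**What the plan says.** Section 3.4.2 of the Protocol is a single sentence. For a participant taken off the intervention early, "the investigator must make every effort to perform the evaluations scheduled for the next assessment phase scheduled for that participant". Section 3.4.1 sends anyone who meets discontinuation criteria during treatment to that procedure. It also says that those who stop treatment "may agree to continue to be followed for additional safety evaluation".

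Other text points towards wider follow-up. Section 3.4.1 states: "The above reasons do not automatically lead to withdrawal from the study in all cases". Section 6.4.2 says that the follow-up questionnaire at 6, 12 and 18 months "is to be completed by each participant". Section 7 says: "Participants in both study arms undergo formal assessment of clinical frailty status at 4 timepoints", namely baseline and months 6, 12 and 18. None of these statements mentions a participant who has stopped the intervention.

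Section 7 makes the onset of clinical frailty an adverse endpoint. The control arm receives no intervention unless a control becomes frail at month 6 or 12. Section 7 describes that exception in two ways: its main text offers such a control the whole suite, while its Important Note provides the physical package.

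**The concern.** The trigger in 3.4.2 is stopping the intervention, not leaving the study. The instruction nevertheless asks for one visit, and the only continuing follow-up mentioned nearby is optional and for safety. A site that follows 3.4.2 exactly may end outcome collection after that visit, and different sites may read it differently.

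Two features make this more than a loss of numbers. First, the reasons for stopping in 3.4.1 (adverse events, medical conditions, lack of efficacy) are plausibly related to frailty. Second, the trigger acts mainly on one arm, because a control never given access has no intervention to stop. For such a control 3.4.2 states no assessment at all.

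If those who stop are at higher risk of frailty, and control losses are smaller or less selective, the intervention participants still measured are the healthier ones and the comparison favours the intervention. If those who stop are at lower risk, or controls are lost in larger numbers, the bias is nil or reversed. A missing-data model can use the one required visit, but no analysis plan can recover an 18-month outcome that was never measured.

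**Working it through.** The protocol states no dropout rate or frailty rate, so there is no figure of its own to reproduce. The check has two parts: which visits the rule leaves unrequired, and an illustration of scale.

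**1. The rule applied to the 6, 12 and 18-month schedule**

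| Participant stops | Visit required by 3.4.2 | Visits not required |
|---|---|---|
| before month 6 | 6 | 12 and 18 |
| months 6-12 | 12 | 18 |
| after month 12 | 18 | none |

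**2. How many participants**

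From the protocol: 25 per arm (Section 4). Assumed: a share d = 0.20 to 0.30 of the intervention arm stops, evenly over the three six-month intervals, and nobody attends voluntarily after the required visit.

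- Unmeasured at 18 months: u = 2d/3 = 0.133 to 0.200, which is 3.3 to 5.0 of 25.
- Unmeasured at 12 months: d/3 = 0.067 to 0.100, which is 1.7 to 2.5 of 25.

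**3. Spurious difference at 18 months**

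Further assumptions: no true effect, true frailty risk p = 0.25 in both arms, no control loss. Let RR be the risk in the unmeasured divided by the risk in the measured. If m is the risk in the measured, then p = (1 - u)m + u·RR·m, so m = p / ((1 - u) + u·RR). The difference is m - 0.25 in percentage points; a negative value favours the intervention.

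| RR | u = 0.133 | u = 0.200 |
|---|---|---|
| 0.5 | 0.25/0.933 = 0.268 (+1.8) | 0.25/0.900 = 0.278 (+2.8) |
| 1 | 0.250 (0) | 0.250 (0) |
| 2 | 0.25/1.133 = 0.221 (-2.9) | 0.25/1.200 = 0.208 (-4.2) |
| 3 | 0.25/1.267 = 0.197 (-5.3) | 0.25/1.400 = 0.179 (-7.1) |

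**4. Sensitivity, RR 2 to 3**

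- Control loss half as large and equally selective: -1.4 to -3.0 points.
- Control loss equal: 0.
- Control loss 1.5 times as large: +1.2 to +2.2, against the intervention.
- p = 0.10: -1.2 to -2.9. p = 0.40: -4.7 to -11.4.
- Half of the unmeasured refuse all follow-up: -1.6 to -4.2 remains after the fix, so the fix removes only 1.4 to 3.0 points.

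**5. Precision**

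At p = 0.25 the standard error of the difference with 25 per arm is sqrt(2 × 0.25 × 0.75/25) = 0.122. With 21.7 or 20 measured against 25 it is 0.127 or 0.130, which is 3.8% or 6.1% larger whatever the direction of any bias.

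**The case against.** The strongest reply is that 3.4.2 describes a closing visit for someone being withdrawn, and that the general schedule covers everyone else by default. Section 3.4.1 separates stopping from leaving the study, and Sections 6.4.2 and 7 cover each participant and both arms. This is a fair reading, and the text sets a minimum, not a ban. But the only instruction written specifically for someone who stops the intervention names the next visit alone, which would be unnecessary if the full schedule plainly continued. Text that supports both readings needs repair.

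The consent forms (Appendices 1-3) were not available for this review and may say what follow-up continues. That limits the claim to the visible text. Even so, 3.4.2 is the site's operating instruction and should state the rule itself.

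It can also be said that safety follow-up might include frailty, since Section 7 calls frailty an adverse endpoint. That is possible, but the text does not say so, and the follow-up remains optional.

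The objection to the size has force. Every input beyond the arm size is assumed. The no-control-loss case is only one scenario, and controls who leave have even less required of them. Low use of the platform need not count as discontinuation. At p = 0.25 even 3-7 points is below one standard error of about 12 points. These arguments limit what can be claimed about bias, but they do not supply the missing requirement.

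**Conclusion.** The concern holds and should be fixed. As written, the plan does not require the 18-month outcome for anyone who stops the intervention before month 12, nor the 12-month outcome for anyone who stops before month 6. Those who stop later lose nothing. This conclusion rests on the visible text alone.

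The effect on the result cannot be derived. The protocol gives no stopping rate, and on frailty in controls Section 7 says: "We cannot estimate or predict what proportion of the control participants may develop frailty during the 18 month trial". Under the stated assumptions about 3-5 of 25 intervention participants are unmeasured at 18 months. The resulting difference then runs from 2-3 points against the intervention, through nil, to 5-7 points in its favour, depending on who stops, and it shrinks, vanishes or reverses as control loss grows. The 4-6% increase in standard error does not depend on direction. Confidence is medium: the gap in the text is clear, its consequence is not.

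**What to change.** Reword 3.4.2 to say that stopping the intervention is not withdrawal from the study, and that every effort will be made to complete all remaining scheduled assessments to month 18, in both arms. Keep two exceptions: the participant withdraws consent to follow-up, or the investigator judges, on the ground already in 3.4.1, that "continued participation in the study would not be in the best interest of the participant in the opinion of the investigator". Record the date and reason for stopping the intervention separately from the date and reason for leaving the study.

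As a side point, reconcile the two statements in Section 7 on what a control who becomes frail receives; this review does not choose between them. Record the date and content of any access given, since such a control then has an intervention to stop.

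The cost is wording plus retention effort for visits already scheduled. Table 6 allows 135 minutes at month 12 and 155 at month 18. A stop before month 6 therefore adds at most 135 + 155 = 290 minutes, and a stop in months 6-12 adds 155. With 20-30% of 25 stopping evenly, 1.7-2.5 people fall in each group. That is 5.0-7.5 visits and 742-1,113 minutes, or about 12-19 hours in the intervention arm. The change cannot recover people who refuse all follow-up.
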